#### 5.8. Analysis of Other Variables

The summary of other variables will be presented separately for the double-blind and open-label period. The double-blind period will be presented by treatment groups (alirocumab, placebo) on the safety population. The open-label period will be presented by all patients and by treatment group of the double-blind period (i.e., alirocumab, placebo) on the open-label population. No formal inferential testing will be performed for either period. Summaries will be descriptive in nature. All summaries of safety results described below will be presented for each period respectively, unless otherwise noted.

All measurements, scheduled or unscheduled, fasting or not fasting, will be assigned to analysis windows in order to provide an assessment for week 4 to week 24 time points.

Hs-CRP parameter ([Section 4.8](#)) will be summarized for the number of patients with data, mean, SD, median, minimum, maximum, Q1 and Q3 by analysis visit during the treatment period. The medians (with Q1-Q3) will be plotted for hs-CRP. Applying the PCSA criteria at any time during the TEAE period, the number of patients (and percentages) meeting the criteria will be summarized.

Binary endpoints defined in [Section 4.8](#) will be described through patient counts and percentages.

The change in the proportion of patients who meet US apheresis eligibility criteria from baseline to week 12 ([Section 4.8](#)) will be summarized by treatment group on the safety population for the number of patients with data, mean, SD, median, minimum, and maximum. The change in the proportion of patients who meet German apheresis eligibility criteria from baseline to week 12 will be summarized in a similar manner.

Correlations between HoFH genotype status and lipid parameters will be explored (e.g., scatter plot).

#### 5.9. Analysis of Anti-alirocumab Antibody Variables

The summary of ADA variables will be presented separately for the double-blind and open-label period. The double-blind period will be presented by treatment groups (alirocumab, placebo) on the ADA population. The open-label period will be presented by all patients and by treatment group of the double-blind period (i.e., alirocumab, placebo) on the open-label population. No

formal inferential testing will be performed for either period. Summaries will be descriptive in nature.

ADA variables will be summarized, taking into account all samples regardless of timing in relation to injections. ADA results will be summarized as follows:

- ADA results (negative or positive) by time point
- Neutralizing status (negative or positive) by time point for positive ADA
- ADA titers using descriptive statistics (median, minimum and maximum) for positive ADA by time point
- Number (%) of patients with pre-existing ADA and number (%) of patients with treatment-emergent ADA positive response
- Number (%) of patients with persistent/indeterminate/transient treatment-emergent ADA positive response (only for the double-blind period)
- Time to onset of treatment-emergent ADA positive response using descriptive statistics.

Correlations between ADA parameters (e.g., titers, treatment-emergent ADA positive status, neutralizing status) and safety and/or efficacy endpoints will also be explored (e.g., scatter plot).

## 5.10. Analysis of Pharmacokinetic Data

Concentrations of total alirocumab in serum and total and free PCSK9 concentrations will be summarized on the PK population by treatment group and visit using descriptive statistics. Descriptive statistics could be provided by specific sub-groups (e.g., gender, BMI, age), as needed.

Time profile for concentrations of total alirocumab and total and free PCSK9 will be provided by treatment group using graphs (mean  $\pm$  SD or Median, as appropriate). Plots of the individual concentrations of alirocumab, and total and free PCSK9 may be presented versus actual time. Additional plots will be prepared, as deemed necessary (e.g., to explore the relationship with some safety or efficacy endpoints of interest).

Concentrations of total alirocumab in serum and PCSK9 levels might be used for population PK modeling if considered necessary and the results of population PK modeling will be reported separately from the study report.

## 5.11. Analysis of Genomics Variables

Plans for the analysis of genomics data will be provided in a separate SAP.

## 5.12. Analysis of Quality-of-Life Variables

The summary of quality-of-life variables will be presented separately for the double-blind and open-label period. The double-blind period will be presented by treatment groups (alirocumab, placebo) on the quality-of-life safety population. The open-label period will be presented by all patients and by treatment group of the double-blind period (i.e., alirocumab, placebo) on the open-label population. No formal inferential testing will be performed for either period.

Summaries will be descriptive in nature. All summaries of safety results described below will be presented for each period respectively, unless otherwise noted.

The analysis of data from EQ-5D instrument will be performed on the quality-of-life population. Baseline is defined as the visit at Day 1 or Visit 3 (week 0) evaluation. Analysis windows for efficacy parameters will be used to assign time point visits.

### *Individual EQ-5D items*

Response for each one of the 5 EQ-5D items will be summarized for each treatment group using tables which will contain frequency and percentage of the patients reporting level 1 (no problems), level 2 (some problems) and level 3 (extreme problems) by analysis visit during the treatment period.

### *EQ-5D utility score*

The raw value and the change from baseline of the utility score will be summarized using mean, median, Q1, Q3, SD, minimum and maximum for each post-baseline visit during the treatment period. Cumulative distribution functions for the change in utility score from baseline will be displayed by treatment groups at weeks 12 on the quality-of-life safety population.

## 6. DATA CONVENTIONS

The following analysis conventions will be used in the statistical analysis.

### 6.1. Definition of Baseline for Efficacy and Safety Variables

Unless otherwise specified, the baseline assessment is programmatically defined as the latest available measurement taken before first administration of double-blind study treatment. For patients randomized but not-treated, the baseline will be the last available measurement before randomization.

### 6.2. Data Handling Conventions for Efficacy Variables

Data handling conventions, including addressing missing data, is addressed for the efficacy endpoints in [Sections 5.6.1](#) and [5.6.2](#).

### 6.3. General Data Handling Conventions

In general, the following formulas will be used for computation of parameters:

#### *Time from diagnosis*

Time from diagnosis (years) = (Date of informed consent – Date of diagnosis\*) / 365.25.

(\*):In case the month of diagnosis would be missing, it will be put equal to JANUARY if the year of diagnosis equals the year of informed consent; it will be put equal to JUNE otherwise. In the case the day is missing, the day will be put equal to 1st if the month and year of diagnosis equals the month and year of informed consent; otherwise it will be put equal to the 15th of the month.

#### *Date of last dose of study treatment*

The date of the last injection is equal to the last date of administration reported on injection administration case report form page, or missing if the last administration date is unknown.

#### *Renal function formulas*

Estimated GFR will be derived using the Modification of the Diet in Renal Disease (MDRD) equation:

$186.3 \times (\text{creatinine in } \mu\text{mol/L} / 88.4)^{-1.154} \times (\text{age in years})^{-0.203} \times 0.742 \text{ if female, } \times 1.21 \text{ if race is "black or African American"}$ .

### ***Lipids variables, laboratory safety variables, hs-CRP***

For data below the lower limit of quantification (LLOQ) / limit of linearity, half of the lower limit value (i.e., LLOQ/2) will be used for quantitative analyses. For data above the upper limit of quantification (ULOQ) / limit of linearity, the upper limit value (i.e., ULOQ) will be used for quantitative analyses.

## **6.4. General Missing Data Conventions**

For categorical variables, patients with missing data are not included in calculations of percentages unless otherwise specified. When relevant, the number of patients with missing data is presented.

### ***Handling of baseline definition if “time” of first double-blind study treatment administration or time of assessment at week 0 visit is missing***

If the time of the first double-blind study treatment administration or the time of assessment at week 0 visit is missing, then the baseline value is defined as the last available value obtained before or on the day of the double-blind first study treatment administration.

### ***Handling of computation of treatment duration and compliance if study treatment first or end of treatment date is missing***

If the last or first injection date is missing, the exposure duration and compliance will be left as missing.

### ***Handling of safety and efficacy analysis periods and survival analysis if end of study treatment date is missing***

If the last injection date for a treatment period (double-blind or open-label) is missing, then this date is imputed to the earliest between

- the last day of the month and year, when applicable or else the 31st of December of the year,
- the date of the end of treatment visit for the respective treatment period:
  - double-blind treatment period: week 12 visit for completer, early end of double-blind treatment visit for patients who prematurely discontinued the study treatment,
  - open-label treatment period: week 24 visit for completer, early end of open-label treatment visit for patients who prematurely discontinued the study treatment,
- the date of the last contact for the purpose of safety and efficacy analysis period start and/or end.

### ***Handling of medication missing/partial dates***

No imputation of medication start/end dates or times will be performed. If a medication date or time is missing or partially missing and it cannot be determined whether it was taken prior or concomitantly, it will be considered a prior, concomitant, and post-treatment medication.

### ***Handling of adverse events with missing or partial date/time of onset, worsening, seriousness***

Missing or partial AE dates and times will be imputed so that if the partial AE date/time information does not indicate that the AE started prior to treatment or after the TEAE period, the AE will be classified as treatment-emergent. These data imputations are for categorization purpose only and will not be used in listings. No imputation is planned for date/time of AE resolution.

### ***Handling of adverse events when date and time of first study treatment administration is missing***

When the date and time of the study treatment administration is missing, all AEs that occurred on or after the day of randomization will be considered as TEAEs.

When the time of the first study treatment administration is missing, all AEs that occurred on the day of the first study treatment administration will be considered as treatment-emergent AEs.

### ***Handling of missing assessment of relationship of adverse events to investigational medicinal product***

If the assessment of the relationship to study treatment is missing, then the relationship to study treatment has to be assumed as possibly related in the frequency tables, but no imputation should be done at the data level.

### ***Handling of potentially clinically significant abnormalities***

If a patient has a missing baseline value he will be grouped in the category “normal/missing at baseline.”

For PCSAs with 2 conditions, one based on a change from baseline value and the other on a threshold value or a normal range, with the first condition being missing, the PCSA will be based only on the second condition.

For a PCSA defined on a threshold and/or a normal range, this PCSA will be derived using this threshold if the normal range is missing; e.g., for eosinophils the PCSA is  $>0.5$  GIGA/L or  $>ULN$  if  $ULN \geq 0.5$  GIGA/L. When ULN is missing, the value 0.5 should be used.

Measurements flagged as invalid by the laboratory will not be summarized or taken into account in the computation of PCSA values.

## 6.5. Visit Windows for Time Points

Visit windows will be programmatically imposed on those efficacy and safety measures repeatedly collected over the course of the study. These visit windows are derived from the number of days in study, specifically assigning day ranges to mimic the study assessment schedule provided in the protocol. Data analyzed by time point (including efficacy, laboratory safety data, vital signs, ECG, quality of life, PK and ADA) will be summarized using the analysis windows given in [Appendix 10.2](#). These analysis windows will be applicable for all analyses, and they are defined to provide more homogeneous data for time point-specific analyses. If multiple valid values of a variable exist within an analysis window, the nearest from the targeted study day will be selected. If the difference is a tie, the value after the targeted study day will be used. If multiple valid values of a variable exist within a same day, then the first value of the day will be selected when time is available, else the scheduled visit will be selected.

## 6.6. Unscheduled Assessments

For efficacy, safety laboratory data, vital signs, ECG, and ED-5D, unscheduled visit measurements may be used to provide a measurement for a time point, a baseline, a last or a worst value, if appropriate according to their definitions. The measurements may also be used to determine abnormal values and PCSA.

## 6.7. Pooling of Centers for Statistical Analyses

The randomization scheme was not stratified by center because the primary efficacy variable is centrally assessed and expected not to be influenced by the center when other factors such as diet are already controlled. Therefore, the center will not be added as factor in the primary analysis model.

## 6.8. Statistical Technical Issues

Not Applicable.

## 7. TIMING OF STATISTICAL ANALYSES

Efficacy and safety analyses for this study will be performed in two steps, specifically for patient data collected up to the time the last patient completes efficacy assessments at week 12 (step 1 consisting of the double-blind period) and at the end of the study (step 2 for the open-label period). No formal interim analysis for efficacy is planned since analyses of primary and key secondary efficacy endpoints will be final at the time of first-step analysis. Therefore, no multiplicity adjustment for multiple analyses is needed (see [Section 5.6.3](#)). The timing for patient data to be reported is defined below for each step:

- First-step: efficacy analyses up to week 12 and interim safety analysis
  - This analysis will be conducted on all randomized patients when all patients will have all their lipid data up to week 12 analysis window collected and validated.
  - The efficacy analyses will be performed up to week 12 time point. Analyses of endpoints up to week 12 time point will correspond to the final analyses for these endpoints. Analysis of lipid parameters beyond week 12 will be descriptive.
  - The safety analyses will be performed on all safety data (double-blind and open-label) collected up to the common cut-off date. For this analysis, the common cut-off date is defined as date of the last week 12 visit.
- Second-step: final analysis
  - This analysis will be conducted at the end of the study and will consist of the final analysis of efficacy data at time points beyond the week 12 time point and final safety analysis.

Individuals involved in the first-step analysis of the study will not be involved in the conduct of the study afterwards; individual patient identification will not be released to anyone who is directly involved in the conduct of the study. The first-step analysis process, the measures used to protect the blind and the integrity of the study, the communication plan, and the confidentiality agreement will be described in a separate document. The results of the first analysis will not be used to change the conduct of the ongoing study in any aspect. The first analysis will be used for the submission dossier to health authorities.

Analyses methods and conventions described in the other sections of this SAP will be applied for all analyses as applicable. The following additional rules will apply for analyses performed at first-step analysis:

- Any lipid assessments within analysis windows up to week 12 will be taken into account (may include few unscheduled lipid data soon after the cut-off date).

- Patients without end of treatment visit (double-blind or open-label) performed at the time of the cut-off date will be considered as ongoing and exposed up to the cut-off date. Therefore:
  - Patients who did not complete the respective treatment period nor prematurely discontinued the study treatment at cut-off date will be analyzed as “ongoing” in the disposition summary.
  - Their TEAE period and treatment period will end at the cut-off date.
  - Their treatment duration will be derived by considering date of cut-off as last injection date.
- Analyses of number of injections, mean injection frequency, percentage of days with under/above-planned dosing and compliance will be performed up to the last injection reported in the e-CRF up to the cut-off date.
- AEs occurring, worsening or becoming serious after the cut-off date will not be included in the analyses. However, any available outcome before database lock, regardless of timing in relation to the cut-off date, of an adverse event starting prior to the cut-off date will be taken into account. Medications, treatment discontinuations/completions and deaths occurring after the cut-off date will not be included in the analyses.
- Post-treatment period, post-study period are not applicable for ongoing patients. Analyses of post-treatment AEs, post-study deaths and post-treatment medications will be performed for patients who either completed or prematurely discontinued the treatment before or at the cut-off date.
- Analysis of status at last study contact and proportion of patients with insufficient follow-up will be provided for patients who either completed or prematurely discontinued the treatment before or at the cut-off date.

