#### **4.5. Study Treatment Exposure and Compliance Variables**

Study treatment exposure variables for injections administered during the double-blind period are listed below with associated definitions:

- Duration of double-blind study treatment exposure in weeks defined as: (last double-blind study treatment administration date +14 – first double-blind study treatment administration date)/7, regardless of unplanned intermittent discontinuations. Values will be rounded to one decimal place.
- The total number of double-blind study treatment injections by patient.
- The following categories will be used for treatment exposure intervals:  $\geq 1$  day and  $<4$  weeks,  $\geq 4$  weeks and  $<8$  weeks,  $\geq 8$  weeks and  $<10$  weeks,  $\geq 10$  weeks.

Study treatment exposure variables for injections administered during the open-label period are listed below with associated definitions:

- Duration of open-label study treatment exposure in weeks defined as: (last open-label alirocumab treatment administration date +14 – first open-label alirocumab treatment administration date)/7, regardless of unplanned intermittent discontinuations. Values will be rounded to one decimal place.
- The total number of open-label alirocumab treatment injections by patient.
- The following categories will be used for treatment exposure intervals:  $\geq 1$  day and  $<4$  weeks,  $\geq 4$  weeks and  $<8$  weeks,  $\geq 8$  weeks and  $<10$  weeks,  $\geq 10$  weeks.

Study treatment exposure variables combining double-blind and open-label periods are listed below for all patients who received alirocumab in the double-blind period:

- Combined duration of alirocumab exposure in weeks defined as: double-blind treatment exposure plus open-label treatment exposure, regardless of unplanned intermittent discontinuations.
- Combined total number of alirocumab treatment injections by patient defined as: total number of double-blind injections plus total number of open-label injections for each patient.
- The following categories will be used for treatment exposure intervals:  $\geq 1$  day and  $<4$  weeks,  $\geq 4$  weeks and  $<8$  weeks,  $\geq 8$  weeks and  $<12$  weeks,  $\geq 12$  weeks and  $<16$  weeks,  $\geq 16$  weeks and  $<20$  weeks,  $\geq 20$  weeks and  $<22$  weeks,  $\geq 22$  weeks.

Compliance will be assessed using the variables below with associated definitions.

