### 5.5.1. Exposure to Investigational Product

Study treatment exposure for the double-blind period will be descriptively summarized for the treatment duration and patient injection total variables listed in [Section 4.5](#). Treatment duration

will be summarized using the number of patients with data, mean, SD, median, minimum and maximum.

For the open-label period, study treatment exposure will be descriptively summarized for the treatment duration and patient injection total variables listed in [Section 4.5](#). Alirocumab dosing exposure in the open-label period will be summarized for all patients in the open-label population. Additionally, alirocumab dosing exposure will be summarized combining double-blind and open-label periods for patients who received alirocumab in the double-blind period.

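### At the first-step analysis, ongoing patients' open-label and combined exposure is credited about two weeks past the cut-off, because the cut-off replaces the last injection date and 14 days are then added (minor)

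*SAP*

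**What the plan says.** SAP 7 (Timing of Statistical Analyses) sets extra rules for the first-step analysis, whose cut-off is the date of the last Week 12 visit. A patient with no end-of-treatment visit by then "will be considered as ongoing and exposed up to the cut-off date". Two consequences are drawn from this:

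- For the observation periods, the SAP says: "Their TEAE period and treatment period will end at the cut-off date".
- For the exposure variable, it gives the rule at issue here: "Their treatment duration will be derived by considering date of cut-off as last injection date".

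SAP 4.5 defines open-label duration in weeks by the formula ending "last open-label alirocumab treatment administration date +14 – first open-label alirocumab treatment administration date)/7". The double-blind formula has the same form, "last double-blind study treatment administration date +14 – first double-blind study treatment administration date)/7". Combined exposure is the sum of the two.

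SAP 5.5.1, which points back to 4.5, shows that treatment duration in SAP 7 means this variable: "study treatment exposure will be descriptively summarized for the treatment duration and patient injection total variables listed in". SAP 7 also carries the conventions of the other SAP sections into the first step where they apply.

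On the use of the results, SAP 7 says: "The first analysis will be used for the submission dossier to health authorities".

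**The concern.** The duration rule is presented as following from the statement that exposure ends at the cut-off, but it does not deliver that. A programmer who puts the cut-off into the SAP 4.5 formula obtains an exposure that ends 14 days later. The extra time lies after the end of the TEAE period, so the exposure table would cover days on which no event is counted. A patient near the end of open-label treatment would also show more exposure than one who completed every dose on schedule. Injection counts at the first step come from the e-CRF up to the cut-off, so the two halves of the exposure summary would disagree.

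At stake is the accuracy of a descriptive safety-exposure table in a trial of about 74 patients that goes into a submission, with the error in the direction of more exposure.

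**Working it through.** **Inputs.** Double-blind injections run from Day 1 to Day 71, and open-label injections from Day 85 to Day 155, every two weeks (Protocol synopsis and 5.1). Each period is planned as 12 weeks (SAP 2.1). The formula is from SAP 4.5 and the substitution rule from SAP 7. The cut-off is one calendar date, so it falls on a different study day for each patient. Write c for that study day.

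**Planned figures first.** With scheduled dates the formula reproduces the plan:

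- double-blind: (71 + 14 − 1)/7 = 12.0 weeks
- open-label: (155 + 14 − 85)/7 = 12.0 weeks
- combined: 24.0 weeks

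**First-step rule.** For an ongoing open-label patient, duration = (c + 14 − 85)/7. Compare this with:

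- time elapsed to the cut-off: (c − 85)/7
- the ordinary formula with the recorded last injection L, for a patient on schedule: (L + 14 − 85)/7

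| Cut-off day c | Last injection L | First-step rule (weeks) | Elapsed (weeks) | Ordinary formula (weeks) | Excess over ordinary formula, c − L (days) |
|---|---|---|---|---|---|
| 85 | 85 | 2.0 | 0.0 | 2.0 | 0 |
| 113 | 113 | 6.0 | 4.0 | 6.0 | 0 |
| 141 | 141 | 10.0 | 8.0 | 10.0 | 0 |
| 154 | 141 | 11.9 | 9.9 | 10.0 | 13 |
| 155 | 155 | 12.0 | 10.0 | 12.0 | 0 |
| 162 | 155 | 13.0 | 11.0 | 12.0 | 7 |
| 168 | 155 | 13.9 | 11.9 | 12.0 | 13 |

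The overrun past the cut-off is always 14 days. The excess over the ordinary formula depends only on the days since the last dose. The result passes 12 weeks only when c is later than Day 155. Combined exposure on Day 168 is 12.0 + 13.9 = 25.9 weeks against 24.0.

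**Exposure categories.** Let d be the days since the first open-label dose. On schedule and up to the Week 22 dose, the ordinary formula gives 2 × (floor(d/14) + 1) weeks, and the first-step rule gives d/7 + 2. Both reach the open-label cut-points of 4, 8 and 10 weeks at d = 14, 42 and 56. Adding 12 double-blind weeks, both reach the combined cut-points of 16, 20 and 22 weeks on the same days.

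**What uses this duration.** Adverse event percentages use patient counts (SAP 5.7.1). Injection-site reactions are divided by injections (SAP 5.7.1). Any Kaplan-Meier analysis censors at the end of the TEAE period (Protocol 10.4.4.1). Neither document specifies an exposure-time-adjusted event rate.

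**The case against.** The strongest reply is that SAP 4.5 credits every injection with 14 days for every patient, so elapsed time to the cut-off is the wrong yardstick. On dosing days such as 85 and 113, the first-step rule gives exactly what the ordinary formula gives. A reader might infer from the elapsed-time column that a patient gets 2.0 weeks for nothing, or is inflated by half at four weeks. Both figures are the SAP's normal credit for injections actually given. This part of the reply stands, and it limits the excess to 0 to 13 days for an on-schedule patient.

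A reader might also infer that patients are pushed into higher exposure categories. That is true only against elapsed time (8.0 weeks elapsed is classed as at least 10). Against the ordinary formula, an on-schedule patient changes no category.

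Nor do the documents set 12 weeks as a cap. It is the planned length, and the top open-label category is open-ended. The 3-day window on the Week 22 dose (Protocol 8.2.1) can by itself give (158 + 14 − 85)/7 = 12.4 weeks.

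It can also be argued that carrying conventions over only where they apply lets the sponsor drop the 14 days. But SAP 7 names a substitute for the last injection date, and the formula that takes this date is the one with the 14 days in it. The text neither removes them nor caps the result. The contradiction with exposure ending at the cut-off therefore remains, and so does the Day 168 result of 13.9 weeks beside six open-label injections.

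**Conclusion.** Wrong as written, but minor. For patients ongoing at the cut-off, first-step open-label and combined exposure ends 14 days after the date at which SAP 7 says it ends. Measured against the SAP's own formula with recorded injections, the overstatement is 0 to 13 days. If the cut-off is equally likely on any day of the dosing interval, the average is (0 + 1 + … + 13)/14 = 6.5 days.

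These figures assume on-schedule dosing and a Week 24 visit on Day 169. A missed latest dose or a late visit increases the excess: a patient still unvisited on Day 171 shows (171 + 14 − 85)/7 = 14.3 weeks, 16 days over. The number of patients affected depends on recruitment in the last 12 weeks, which the documents do not give.

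A reader might infer biased event rates or a distorted randomised comparison. The documents do not support that:

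- No planned event rate uses this duration.
- Double-blind exposure is almost untouched, because the cut-off is the last Week 12 visit. Only a patient with no end-of-double-blind visit would be caught.
- Efficacy and the second-step analysis are unaffected.

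**What to change.** In SAP 7, replace the substitution with one rule for all patients at the first step, and carry it into combined exposure:

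duration = (the earlier of [recorded last injection date + 14] and [cut-off date + 1] − first injection date)/7

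For the Day 168 patient both limits are Day 169, so (169 − 85)/7 = 12.0 weeks, equal to an on-schedule completer. Exposure never runs past the cut-off and never credits more than the injections in the e-CRF support.

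Dropping the 14 days for ongoing patients only would be worse. Take two patients with injections on Days 85 and 99 and a cut-off on Day 99. The one who had discontinued would get (99 + 14 − 85)/7 = 4.0 weeks, and the ongoing one (99 − 85 + 1)/7 = 2.1. The single rule gives both (100 − 85)/7 = 2.1.

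The cost is one sentence, one line of programming and smaller interim figures. An on-schedule ongoing patient loses (c + 14) − (c + 1) = 13 days against the present rule. Some would then sit in a lower category: on Day 141, (142 − 85)/7 = 8.1 weeks instead of 10.0. The SAP 4.5 formula stays as it is for the second step.
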